## 13.2 Secondary Efficacy Analyses

Secondary outcomes will be analysed as appropriate (according to the distribution of each outcome), comparing the difference between groups at the specified follow-up visit and relative to baseline value (where specified/measured). Baseline variables predictive of each outcome (the measure at baseline where available), and stratifying

SCOPE-BD NUIG-2017-002, Statistical Analysis Plan Version 1, 19/03/2024  
variables will be included in ANCOVA or generalised linear models of outcome variables.

For secondary outcomes, the focus will be on the point estimates and confidence intervals for hypothesis generation.

Additional analysis of the primary outcome will compare the time course of HDRS under placebo and treatment using a mixed-effects model including fixed-effects terms for time since randomisation/study visit, trial arm and their interactions, and a random effect to account for correlation of multiple observations per participant.

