## 7 Sample Size

The primary outcome in this study is the Hamilton Depression Rating Scale score (HDRS). It is judged that a decrease of 50% or more in the HDRS score between randomisation and Visit 6 will be sufficient to consider a patient to have experienced a response. We anticipate that the average HDRS score in the proposed population pre-randomisation will be 24 units and that this outcome variable will be approximately normal. Based on results from the literature, it is estimated that a range of plausible values for the standard deviation is between 5 to 13 units.

SCOPE-BD NUIG-2017-002, Statistical Analysis Plan Version 1, 19/03/2024

Using this information, a sample of 44 participants (22 in each group) will have 85% power to detect a difference of 12 units between the treatment and control arms, i.e. an expected HDRS mean score of 12 in the treatment group vs. an expected HDRS mean score of 24 in the control group after Visit 6. The sample size is based on a 2-sample t-test (two-sided) with a standard deviation of 13 units (conservative approach) and a significant level of 0.05. Allocating 25 participants to each arm will ensure power  $\geq 85\%$  when loss to follow-up is  $< 12\%$  (6 participants missing at Visit 6 follow up).

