# 13 Efficacy Analyses

## 13.1 Primary Efficacy Analysis

For the primary effectiveness analysis of the primary outcome, it is expected that pre-randomisation measurements of the HDRS score will be correlated with the scores obtained at Visit 6 of treatment. The mean scores at Visit 6 will be compared across the study arms using an ANCOVA model. The response variable will be the change in HDRS score from Visit 3 to HDRS at Visit 6 including the HDRS score at Visit 3 as a covariate in the model.

The addition of stratifying variables and other variables as covariates will be considered as appropriate. This analysis will increase the power to detect significant differences between the groups.

Inverse probability weighting will be applied to the primary outcome analysis. These weights will be derived based on the inverse of the probability of a patient's data being missing given their pre-randomisation measurements. This will ensure the estimate and inference is more representative of all patients randomised, reducing bias in the estimation of the treatment effect due to participants lost to follow-up and missing data.

Inference regarding the treatment effectiveness will focus on the point estimate, confidence interval and p-value for hypothesis confirmation.

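### The HDRS time-course model in SAP 13.2 lists no baseline adjustment; with categorical visits this costs precision that the primary ANCOVA keeps, and the repair is nearly free

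*SAP*

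**What the plan says.** The primary analysis (SAP 13.1) is an ANCOVA of change in HDRS from Visit 3 to Visit 6, "including the HDRS score at Visit 3 as a covariate in the model". The reason given is that "it is expected that pre-randomisation measurements of the HDRS score will be correlated with the scores obtained at Visit 6 of treatment", and the section says that the adjustment raises power. Inverse probability weights are applied to this analysis.

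SAP 13.2 then adds a time-course analysis of HDRS "using a mixed-effects model including fixed-effects terms for time since randomisation/study visit, trial arm and their interactions", with "a random effect to account for correlation of multiple observations per participant". Protocol 11.5.2 describes the model in the same terms. Neither text says:

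- whether Visit 3 is an outcome row;
- whether time is a category or a continuous variable;
- which contrast gives the effect at a visit;
- whether Visit 3 HDRS or the randomisation stratum enters the model.

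Earlier in SAP 13.2, "Baseline variables predictive of each outcome (the measure at baseline where available), and stratifying" variables are assigned to ANCOVA or generalised linear models of the secondary outcomes. The mixed model is not named there. SAP 10.5 classes everything beyond the primary analysis as exploratory.

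**The concern.** The plan's own argument for adjusting the primary analysis applies equally to the repeated HDRS scores, yet the listed terms of the time-course model make no use of it. Taken as written, with visit as a category, the arm effect at each visit is one of two unadjusted contrasts: a difference in change scores if Visit 3 is an outcome row and the interaction is reported, or a difference in raw means if Visit 3 is left out.

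The stated interest is in a rapid effect. Visit 4 holds the first HDRS score after a randomised infusion. SAP secondary endpoint 5 covers HDRS at Visits 5, 6 and 7 but not Visit 4, so the early contrast depends largely on this model. The trial would also report two Visit 6 HDRS estimates that can differ through chance imbalance at Visit 3, with no stated reason to prefer one.

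**Working it through.** **Inputs from the documents.** SAP 7: difference 12 units, 22 per arm analysed, 25 per arm randomised, 85% power, "with a standard deviation of 13 units (conservative approach) and a significant level of 0.05"; the "plausible values for the standard deviation is between 5 to 13 units". SAP 6.3: 1:1 allocation in blocks of 4 and 6, stratified at HDRS 23. **Assumed:** the correlation r between Visit 3 and later scores, for which the documents give no figure (0.3, 0.5 and 0.7 shown); equal SDs at each visit; complete data.

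**1. The plan's own figure.** A two-sample t-test with 22 per arm, difference 12 and SD 13 has 84.9% power (noncentral t), or 86.5% by the normal approximation. The stated 85% is reproduced, and 44/(1 − 0.12) = 50. There is no design figure for the mixed model.

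**2. Precision with categorical visits.** With n per arm and base variance 2·SD²/n, the variance of the arm contrast at a visit is:

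- raw means (Visit 3 omitted): base × 1
- change scores (Visit 3 an outcome row): base × 2(1 − r)
- ANCOVA: base × (1 − r²)

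The interval-width ratios to ANCOVA are therefore √(2/(1 + r)) for change scores and 1/√(1 − r²) for raw means.

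| r | Change / ANCOVA | Raw means / ANCOVA | SE change | SE raw means | SE ANCOVA |
|---|---|---|---|---|---|
| 0.3 | 1.24 | 1.05 | 4.64 | 3.92 | 3.74 |
| 0.5 | 1.15 | 1.15 | 3.92 | 3.92 | 3.39 |
| 0.7 | 1.08 | 1.40 | 3.04 | 3.92 | 2.80 |

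The SEs are in HDRS points at SD 13 and 22 per arm, where the base SE is 13 × √(2/22) = 3.92.

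**3. Disagreement with an unweighted ANCOVA at Visit 6.** The raw-means contrast differs from ANCOVA by r times the Visit 3 arm difference, and the change contrast by (1 − r) times it, in the opposite direction. With 25 per arm and no stratification, the SE of the Visit 3 difference is 5 × √(2/25) = 1.41 at SD 5 and 13 × √(2/25) = 3.68 at SD 13. At r = 0.5 the disagreement has SD 0.5 × 1.41 = 0.71 or 0.5 × 3.68 = 1.84 points.

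**4. Allowing for stratification.** This was simulated with 25 per arm, mean 24, blocks of 4 and 6, and strata split at 23 on the Visit 3 score.

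| r = 0.5, stratified | SD 5 | SD 13 |
|---|---|---|
| SD of Visit 3 arm difference | 0.89 | 2.3 |
| SD of disagreement with ANCOVA | 0.46 | 1.2 |

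At SD 13 the sampling SEs are 3.18 (ANCOVA), 3.39 (raw means) and 3.35 (change). The ratios are 3.39/3.18 = 1.07 and 3.35/3.18 = 1.05. The nominal intervals, which do not credit the stratification, stay about 15% wider.

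**5. If time is linear instead.** A random-intercept model on days 0, 4, 8, 15 and 29 (SD 13, 22 per arm) was evaluated at day 15. The interaction contrast has SE 2.16, 1.83 and 1.41 at r = 0.3, 0.5 and 0.7, below ANCOVA each time. The total arm difference (arm term plus interaction) has SE 2.66, 3.07 and 3.44, which is below ANCOVA at 0.3 and 0.5 and above it at 0.7. Both are valid only if the arm difference is linear from day 0 to day 29, which is doubtful with randomised infusions near days 0, 4 and 8 and none afterwards.

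**The case against.** **The list is not exhaustive.** The wording introduces the fixed effects as terms the model includes, so a baseline term is not ruled out. That stands: a reader may infer that the plan forbids adjustment, and it does not. It leaves the choice open, and protocol 11.1 promised that the SAP would close it.

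**Baseline may already be used.** Time since randomisation starts at Visit 3, so a Visit 3 outcome row is a natural reading, and the interaction is then a change contrast. This is valid under randomisation and costs only 8% in interval width at r = 0.7. That stands, though at r = 0.3 the cost is 24%.

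**It is not the only HDRS analysis over time.** A reader might infer that baseline information is discarded for the whole course. The documents do not support that. Endpoint 5 at Visits 5 to 7 falls under the sentence in SAP 13.2 that brings in baseline and stratum, and SAP 13.3 mentions a further longitudinal model. Visit 4 is the gap in endpoint 5; the protocol synopsis names that visit only in general terms.

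**Less precise is not a general truth.** Step 5 shows that it depends on the time coding, which the plan leaves open.

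**Baseline is not the only source of disagreement.** The primary ANCOVA is weighted and no weighting is stated for the mixed model, so the two could differ even with perfect balance at Visit 3.

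**The stakes are modest.** The analysis is exploratory, and half a point to 1.2 points is small beside the 12-unit design difference. That sets the weight of the point but gives no reason to leave the precision unused.

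**Conclusion.** The point holds in limited form. As listed, and with categorical visits, the arm contrasts at each visit are unbiased but less precise than baseline-adjusted ones for any correlation between 0 and 1. Nominal intervals are wider by 8 to 24% (Visit 3 an outcome row) or 5 to 40% (Visit 3 omitted) over the assumed correlations of 0.3 to 0.7. With stratification at 23 counted, the true sampling loss at r = 0.5 is about 5 to 7%, and the Visit 6 estimate differs from an unweighted ANCOVA with an SD of roughly 0.5 points (SD 5) to 1.2 points (SD 13).

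These sizes rest on complete data, equal SDs, correlations the documents do not give, and, for the stratified figures, trial-entry HDRS being the Visit 3 score. A reader might take this as bias, or as a threat to the trial's main conclusion. It is neither: randomisation protects the unadjusted contrasts, and the primary estimate, its test and the sample size do not depend on this model. It is a free improvement to an exploratory analysis.

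**What to change.** In SAP 13.2 and protocol 11.5.2, state that visit is categorical and choose one of two forms:

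- (a) outcomes at Visits 4, 5, 6 and 7, with Visit 3 HDRS, its interaction with visit, and the randomisation stratum as covariates; or
- (b) Visit 3 kept as an outcome, with one common Visit 3 mean for both arms (no arm effect at baseline).

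Report the adjusted arm difference with its confidence interval at each visit, and name the Visit 6 contrast. Form (a) brings that contrast to about ANCOVA precision: SE 3.39 rather than 3.92 at SD 13, r = 0.5 and 22 per arm.

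The cost is a sentence or two in each document. No new data are needed, since Visit 3 HDRS and the stratum are already recorded. Form (a) adds five fixed-effect parameters (four visit-specific baseline slopes and one stratum term), which is a small price with 44 to 50 participants; form (b) removes one. A sentence saying that the weighting of the primary analysis is a separate reason for the two Visit 6 estimates to differ would help the reader of the report.

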### 13.3 Other Efficacy Analysis

Sensitivity analyses will be performed on the primary outcome to assess efficacy of getting the treatment (rather than being offered/randomised to treatment) compared to placebo by incorporating the original allocation of participants and their level of adherence to treatment. This will involve examining the short term-effect of treatment in a longitudinal model and the overall effect of number of IV treatments received at follow-up visits after the final IV treatment.

## 14 Safety Analyses

The results of clinical monitoring including blood pressure or heart rate changes, and AEs secondary to phlebotomy or cannulation will be examined between the groups. Adverse events will be coded according to the Medical Dictionary for Regulatory Activities (MedDRA). The incidence of treatment-emergent adverse events will be summarized by system organ class (SOC) and preferred term.

Safety data will be presented primarily in a descriptive fashion. The small sample size and likely low adverse event rates will mean any inference is likely underpowered to detect a range of meaningful differences.

Blinded data will be presented to the DSMB for safety evaluation to coincide with scheduled DSMB meetings.

### 14.1 Drug Exposure

The analysis of drug exposure will include:

- Counts and percentages of participants achieving full dose by visit and treatment group.
- Summaries of the duration of infusion by visit and treatment group.
- Summaries of the overall duration of infusion by treatment group.

A discussion on how drug exposure may be related to the appearance of expected events during the 90 minutes post-infusion will also be provided.

## 14.2 Adverse Events

The analysis of adverse events will include:

- A summary of the number of patients experiencing any adverse event, counts and percentages per group.
- Summaries of the number of patients experiencing each of the adverse events. Summaries will also be reported by severity using the preferred term. Note that if a patient has different severity grades for the same adverse event the highest severity grade will be considered.
- Summaries of patients with AEs related to the treatment by preferred term will be given.
- Summaries of the number of patients experiencing each of the adverse events and the action taken will be given. Summaries will also be reported by severity using the preferred term.

These will be summarised overall, by visit and by treatment group.

## 14.3 Deaths, withdrawal, Serious Adverse Events and other Significant Adverse Events

The analysis of Serious Adverse Events (SAE) will include:

- An overview of the number of SAEs recorded in the study. Specifically, the number of patients experiencing at least one SAE and whether the patient was withdrawn as a result of the SAE. The information will be summarised using counts and percentages.
- Summaries of the number of patients experiencing serious adverse events, by preferred term (counts and percentages).

These will be summarised overall, by visit and by treatment group.

### 14.3.1 *Withdrawal due to Adverse Events*

Withdrawals will be summarised as the number and percentage of patients who were withdrawn from the study including reason for withdrawal as given in the Off Study Form.

### 14.3.2 *Deaths*

In the unlikely event of any deaths, these will be summarised as the number and percentage of patients who died within the study period by treatment arm.

### 14.3.3 Other AE Assessments

No additional Adverse Event Assessments were completed, and no additional analysis is planned.

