8.4.4.1 Vital signs

Vital signs will be recorded for all participants and will include: blood pressure (BP), heart rate (HR) (beats per minute (bpm)), and respiratory rate (RR) (respirations per minute). These will be recorded at screening, Visit 2 and at Visits 3, 4 and 5. Patients will rest for 5 minutes before measurements are obtained. Vital signs will be recorded prior to infusions and post infusions. Prior to infusion vital signs should be obtained post cannulation.

For post infusion vital signs will be taken within 15 minutes post-infusion administration and fifty to 90 minutes post-infusion, resting HR and BP will be measured, with a requirement for a HR ≥ 50 bpm, and BP ≥ 90 mm Hg Systolic and ≥ 60 mm Hg diastolic prior to visit completion. Clinical support is present to support and advise research staff and participants in relation to the management or treatment strategies that are required if the participants HR is < 50 bpm

or > 100bpm or if participant is hypotensive (BP < 90/60). Clinical support includes ready access to resuscitation equipment and clinical expertise.

Where BP and / or HR are abnormal when measured post-infusion the participants respiratory rate will additionally be recorded, and this information will be provided to an on-site clinician.

All participants will be required to remain in the HRB-CRFG for a period of observation by trial staff for a minimum of 90 minutes post infusion. Participants should be asymptomatic of potential IMP related symptoms as well as having satisfactory vital signs before discharge post infusion.

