9.8.2 Prohibited medications

The following medications are contraindicated during the randomised treatment period as they may potentially alter the pharmacokinetics of Scopolamine and any participants newly prescribed these medications at randomisation visit will be excluded from the trial prior to any infusion being administered.

- Physostigmine
- Biperiden
- Procyclidine
- Tricyclic Antidepressants with significant anticholinergic properties (e.g. Amitriptyline and Nortriptyline) that are causing the participant to experience anticholinergic side effects (e.g. blurred vision, constipation, urinary retention, cognitive difficulties).

Participants prescribed any of the above agents during the trial will not receive any further intervention (infusions of Scopolamine or placebo), however will be followed up for the remainder of the trial with data collected included in intention-to-treat analyses if one infusion and one follow-up assessment have been completed.

Participants cannot participate in any other IMP studies while participating in this study (Visits 2-7).

10. Safety reporting

Adverse events will be captured for all study participants from the time of consent for the duration of their participation in the study i.e. from the time of consent to their final study visit. A full AE review at each study visit will ensure that a complete evaluation of the safety and tolerability of the IMP is conducted.

All participants will have their heart rate and blood pressure measured prior to infusion and post-infusion to measure haemodynamic changes, with normal results (see section 8.4.4.1) required post-infusion prior to the participant completing their visit (minimum 90 min monitoring period).

If the readings have not returned to normal within this required 90-minute monitoring period a further period of monitoring will be conducted. A treating investigator must assess and decide if medical intervention is required based on their clinical judgement. Additionally, the PRISE questionnaire (this is optional for participants) will be used where participants agree to document other adverse effects prior to participants completing their clinical visits 2, 3, 4, and 5 (see Section 8.5). All adverse events will be reported to the Sponsor on the AE case report.

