10.2 Evaluation of AEs and SAEs

The investigator or delegate will report all AEs and SAEs to the Sponsor as outlined in section 10.3, except for those identified as outcomes identified below.

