10.2.1.2 Scopolamine infusion related

The following events are considered expected, transient side effects of scopolamine therapy and are therefore exempt from safety reporting if they occur in the 90 minutes post IMP infusion (visit 3, visit 4 or visit 5). These events will be captured on a study outcome form.

- (a) Drowsiness
- (b) Blurred vision
- (c) Dry mouth
- (d) Thirst
- (e) Urinary retention

The above occurrences are considered Adverse events and therefore reportable if any of the following occur:

- medical intervention or treatment
- prolonged monitoring in addition to the 90 minutes post infusion required by the protocol
- deemed medically significant by an investigator
- cessation of the study drug (current or subsequent infusions)

These events must be reported as SAEs/SARs if they meet one or more of the seriousness criteria.

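### Five expected scopolamine effects go on an outcome form instead of the AE record, and the SAP specifies no by-arm count of them

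*SAP*

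**What the plan says.** Protocol 10.2.1.2 lists drowsiness, blurred vision, dry mouth, thirst and urinary retention. It describes them as "considered expected, transient side effects of scopolamine therapy" and makes them "exempt from safety reporting if they occur in the 90 minutes post IMP infusion (visit 3, visit 4 or visit 5"). On where they are recorded it says: "These events will be captured on a study outcome form". They return to the AE record if they need intervention or treatment, are judged medically significant, lead to study drug being stopped, or require "prolonged monitoring in addition to the 90 minutes post infusion required by the protocol". Events meeting a seriousness criterion must be reported as serious. Protocol 10.2 states the general carve-out: AEs go to the sponsor "except for those identified as outcomes identified below".

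SAP 14.2 gives counts and percentages of patients with AEs, overall, by visit and by treatment group. SAP 14.3.3 then says: "No additional Adverse Event Assessments were completed, and no additional analysis is planned". SAP 14.1 promises a discussion of how exposure may relate to expected events in the 90 minutes after infusion. SAP 5.2.2 item 15 is a secondary endpoint for other adverse effects seen on vital signs, reported by participants or measured by PRISE.

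Safety is part of the primary objective (SAP 5.1.1). Safety and tolerability of three infusions against placebo is a secondary objective (SAP 5.1.2).

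**The concern.** The events taken out of the AE table are the ones the protocol itself expects from the drug. Followed literally, the SAP's specified safety count by arm omits every uncomplicated occurrence of them, and 14.3.3 closes the section by saying nothing further was assessed or will be analysed. A reader of the study report could see similar AE percentages in the two arms and conclude that tolerability was similar, while the data that would show otherwise sit untabulated on another form.

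The stake is the descriptive tolerability comparison. The primary efficacy analysis and the sample size are not affected.

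**Working it through.** The plan states no figure on this point, so there is none to reproduce. The check is a reading of the passages, followed by a scale calculation.

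**Step 1: where each effect could be counted by arm.**

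| Place in the plan | What it covers | Specified by-arm count of the five events? |
|---|---|---|
| SAP 14.2 | AEs, so only occurrences that met a trigger | No |
| SAP 14.1 | Discussion of expected events | No table, count or denominator |
| SAP 5.2.2 item 15 with SAP 13.2 | Generic between-group comparison of other adverse effects | Neither the five events nor the form is named; no summary is given |
| SAP 5.2.2 item 8(ii) | VAS before and after infusion; compulsory (protocol 8.5) | Drowsiness only, as a score |
| PRISE | Patient-rated side effects | Optional (protocol 8.5); no summary specified |
| Protocol 7.3.2 item 13 with SAP 8.2 | Bradycardia, hypotension, dizziness, sedation | None of the five terms |
| SAP 14.3.3 | States that nothing additional was done or is planned | No |

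SAP 18 says the outputs will be those based on the analyses the SAP describes, so a table it does not describe is not promised.

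**Step 2: effect on the *any adverse event* row.** The input is 25 patients per arm (protocol synopsis and 8.2.1). Let r be the number in an arm with at least one reportable AE, and e the number whose only events are exempt. S is scopolamine and P is placebo.

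- Difference shown by 14.2: (r_S − r_P)/25
- Difference counting both kinds of event: (r_S + e_S − r_P − e_P)/25
- Amount not shown: (e_S − e_P)/25

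One patient is 1/25 = 0.04, or 4 points. With k = e_S − e_P the hidden difference is 4k points:

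| k | Hidden difference (points) |
|---|---|
| 0 | 0 |
| 1 | 4 |
| 3 | 12 |
| 5 | 20 |

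The documents give no event rates, so k cannot be chosen from them. It is zero if the arms have equal numbers of such patients, or if every patient with an exempt event also has a reportable AE.

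**Step 3: what makes k smaller.** Protocol 8.4.4.1 says: "Participants should be asymptomatic of potential IMP related symptoms as well as having satisfactory vital signs before discharge post infusion". Protocol 17.4.1.4 reports past effects lasting under 3 hours, and monitoring beyond 90 minutes is itself a trigger. Some longer-lasting occurrences will therefore become reportable and appear in 14.2.

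**Step 4: Visit 2.** The exemption names Visits 3 to 5 only, whereas the opening of protocol section 10 says: "Adverse events will be captured for all study participants from the time of consent for the duration of their participation in the study". The same symptom after the saline run-in is therefore an AE. By-visit summaries that include Visit 2 would apply two counting rules to it.

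**The case against.** The strongest reply is that a between-group comparison is already committed and only the detail is missing. Protocol 10.2 treats the exempt events as outcomes, endpoint 15 takes in effects reported by participants, and SAP 13.2 compares secondary outcomes between groups with estimates and confidence intervals. SAP 14 says the results of clinical monitoring will be examined between groups, in wording that is not exhaustive. The 14.1 discussion could hardly be written without tabulating the events. SAP 14.3.3 sits under deaths, withdrawals and serious events. If uncomplicated occurrences are not AEs, its sentence can be read as consistent with an outcome form.

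Much of this stands. A reader might infer that the five effects go wholly unanalysed, or that 14.3.3 flatly contradicts the protocol. The documents support neither: part of the gap is covered, and 14.3.3 has a benign reading. What survives is narrower. Even on that reading, no section names the five events, the form, a summary or a denominator. PRISE, which endpoint 15 uses to measure adverse effects, still does not fit the sentence in 14.3.3.

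A reader might also infer that the Visit 2 mismatch biases the arm comparison. It does not, because Visit 2 precedes randomisation and everyone receives saline. It affects only how figures are read across visits.

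Nor do the documents support treating sedation as drowsiness. Protocol 7.3.2 item 13 lists sedation as its own endpoint item, protocol 8.11 puts it on the Adverse Event Form for patients who withdraw consent during or just after an infusion, and it is not among the five exempt terms.

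**Conclusion.** The point holds as a gap in specification that should be closed. The SAP sets out no by-arm count of the five outcome-form events, and the wording of 14.3.3 discourages one. If these effects are commoner on scopolamine, the *any adverse event* row can understate the tolerability difference.

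The amount cannot be estimated from the documents and may be zero. The 4 points per patient is a scale that assumes 25 per arm in the Safety set; it is not a forecast. A reader might take it as evidence of a large hidden difference, but without event rates that does not follow. SAP 14 already describes safety reporting as primarily descriptive and underpowered for inference, so no confirmatory conclusion changes.

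**What to change.** Replace SAP 14.3.3 with text such as:

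> Expected post-infusion events. For the Safety set, the number and percentage of patients with each of drowsiness, blurred vision, dry mouth, thirst and urinary retention on the study outcome form will be tabulated descriptively by arm, at Visits 3, 4 and 5 and overall. PRISE will be summarised by arm, with the number of patients completing it as denominator.

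Then:
- Refer the 14.1 discussion and endpoint 15 to this table.
- Footnote 14.2 to say that uncomplicated exempt events are excluded at Visits 3 to 5 but not at Visit 2.
- Report sedation separately under protocol secondary endpoint 13, not merged with drowsiness.
- Optionally, add a combined row to 14.2 for any AE or expected post-infusion event.
- Leave the AE and expedited reporting rules as they are.

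The cost is one descriptive table of 5 × (3 + 1) = 20 rows, a footnote and a PRISE summary, all from data the protocol already collects. There is no new hypothesis test and no change in sample size. The downsides are that scopolamine may look less well tolerated, and that PRISE denominators may be small because completing it is optional.
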